6.2 Sample Size Considerations

The primary endpoint will be evaluated in approximately 450 subjects randomized (2:1 sipuleucel-T versus control arm). For each subject, a dichotomous variable defines Gleason group upgrade, with success defined as being free of histopathologic upgrade after 36 months of follow-up. Based on data available, it is estimated that the proportion of histopathologic upgrading by 36 months following randomization for control arm subjects will be approximately 0.30. While there is no prior information on treatment response to sipuleucel-T in early stage disease available, a meaningful hypothesized reduction in this proportion is a reduction by 0.14, giving a projected outcome proportion of upgrading in the sipuleucel-T arm of 0.16.

The null hypothesis is that the proportion free from upgrading at 36 months in both arms is 0.70 (= 1 - 0.3) versus the specific alternative hypothesis of a greater sipuleucel-T arm upgrading-free proportion of 0.84 (= 1 - 0.16). If we denote the proportion free from upgrade at 36 months in the sipuleucel-T arm as p_s and the proportion free of upgrade at 36 months in the control arm as p_c , then the null hypothesis is that

$$H_0: p_s = p_c = 0.70$$

versus the alternative hypothesis

$$H_A: p_s \geq 0.84.$$

Written in terms of the odds ratio, the hypotheses can be depicted as

$$H_0: \frac{\frac{p_s}{(1-p_s)}}{\frac{p_c}{(1-p_c)}} = 1$$

versus the alternative hypothesis

$$H_A: \frac{\frac{p_s}{(1-p_s)}}{\frac{p_c}{(1-p_c)}} \geq \frac{\frac{0.84}{(1-0.84)}}{\frac{0.70}{(1-0.70)}} = 2.25.$$

Based on an overall 1-sided alpha of 0.025, approximately 300 subjects in the sipuleucel-T arm and 150 subjects in the control arm will provide at least 90% power to demonstrate the superiority of sipuleucel-T to control.

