10.1 Sample Size Considerations

The primary endpoint will analyze approximately 450 subjects randomized (2:1 sipuleucel-T versus control arm), and for each subject, is dichotomous with success defined as having been observed to be free of histopathologic upgrade after 36 months of follow-up. Based on data available, it is estimated that the proportion of histopathologic upgrading by 36 months following randomization for control arm subjects will be approximately 0.30. While there is no prior information on treatment response to sipuleucel-T in early stage disease available, a meaningful hypothesized reduction in this proportion is a reduction by 0.14, giving a projected outcome proportion of upgrading in the sipuleucel-T arm of 0.16. The null hypothesis of both arms having a proportion of 0.70 (= 1- 0.3) being free from upgrading at 36 months versus the

specific alternative hypothesis of a sipuleucel-T arm outcome of 0.84 (= 1- 0.16). The odds ratio associated with the specific alternative hypothesis is 2.25 (sipuleucel-T arm odds over control arm odds). Based on an overall 1-sided alpha of 0.025 approximately 300 subjects in the sipuleucel-T arm and 150 subjects in the control arm will provide 90% power to demonstrate the superiority of sipuleucel-T to control.

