10.5 Analysis of Study Endpoints

10.5.1 Primary Endpoint

The primary endpoint is the proportion of subjects without a histopathologic upgrade over the 36-months following randomization and will be summarized by study arm. The primary endpoint for each subject is dichotomous with success defined as having been observed to be free of histopathologic upgrade at Biopsy 2 33 to 39 months after randomization. Histopathologic upgrading occurs when a subject with ISUP Grade Group 1 prostate cancer, at randomization, is upgraded to Grade Group 2 or higher, or a subject with ISUP Grade Group 2 prostate cancer, at randomization, is upgraded to Grade 3 or higher as determined by BICR, at any post-randomization biopsy. Histopathologic status is determined by biopsy and will be assessed at the scheduled biopsy or at any biopsy that is taken during radical-prostatectomy or

other time-point. Subjects upgrading before 36 months, or those found as upstaged at Biopsy 2, or those not observed at 36 months (i.e., do not complete Biopsy 2 prior to 39 months post randomization) will be regarded as failures in the primary analysis.

The primary analysis null hypothesis, $H_0: \Omega \leq 1$, versus the alternative hypothesis, $H_A: \Omega > 1$; where Ω is the odds of success in the sipuleucel-T arm over the odds of success in the control arm. The Cochran-Mantel-Haenszel (CMH) test, stratified by ISUP Grade Group 1 or 2 and the number of biopsies showing the presence of disease prior to registration will be used to estimate the odds ratio, and will be computed using exact methods based on Monte Carlo computations due to the potential for small frequencies.

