A subject has a Gleason group upgrade if they had an ISUP Grade Group 1 at baseline and an ISUP Grade Group 2 or higher within 36 months post-randomization or if they had an ISUP grade group 2 at baseline and an ISUP Grade Group 3 or higher within 36 months post-randomization. The primary endpoint is the proportion of subjects in the treatment arm without ISUP Gleason group upgrade within 36 months of randomization. That is, success for this endpoint is defined as not having a Gleason group upgrade at Biopsy 1 or Biopsy 2, after being assessed at least through 36 months (Biopsy 2). Subjects upgrading before 36 months, those with an upgrade at Biopsy 2, or those with missing ISUP grade group at baseline or Biopsy 2 will be counted as failures.

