12.6.1.1 Methods for Handling Dropouts and Missing Data

Missing baseline or post-baseline ISUP grade group will result in imputed failure status as defined in [Section 8.1.1](#). These methods allow for a conservative estimate of the proportion that do not have ISUP grade group upgrade if information is not available to determine no upgrade. The pattern of missingness across study treatment arms will be explored using a Kaplan-Meier plot of missing ISUP grade group assessments across time.

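### The stated 90% power is for upgrading alone, but the primary analysis also counts upgrade-free men without a usable Biopsy 2 grade as failures, with no allowance

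*SAP*

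**What the plan says.** **Power statement.** SAP 6.2 assumes that "the proportion of histopathologic upgrading by 36 months following randomization for control arm subjects will be approximately 0.30", with 0.16 in the sipuleucel-T arm. Success is taken as one minus these, 0.70 and 0.84, an odds ratio of 2.25. With one-sided alpha 0.025 it concludes that "approximately 300 subjects in the sipuleucel-T arm and 150 subjects in the control arm will provide at least 90% power". Protocol 10.1 and the synopsis use the same inputs; Protocol 10.1 says "300 subjects in the sipuleucel-T arm and 150 subjects in the control arm will provide 90% power to demonstrate the superiority" of sipuleucel-T.

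**Success in the sample size sections.** SAP 6.2 has "success defined as being free of histopathologic upgrade after 36 months of follow-up". Protocol 10.1 has "success defined as having been observed to be free of histopathologic upgrade after 36 months of follow-up", so it requires observation, yet it still uses the upgrading-only rates.

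**Failure in the primary analysis.** Protocol 10.5.1 says that "those not observed at 36 months (i.e., do not complete Biopsy 2 prior to 39 months post randomization) will be regarded as failures". SAP 8.1.1 says that "those with missing ISUP grade group at baseline or Biopsy 2 will be counted as failures", and SAP 12.6.1.1 repeats the rule: "Missing baseline or post-baseline ISUP grade group will result in imputed failure status". The analysis set is all randomised men (SAP 9.1) and the test is an exact stratified Cochran-Mantel-Haenszel (CMH) test (SAP 12.6.1).

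**Limited substitution.** Under SAP 8.1.1 a missing Biopsy 2 grade can be filled from another centrally reviewed biopsy, but only one within 90 days of the 36-month visit.

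Neither document states an expected missing-biopsy or dropout rate, or an inflation of the 450.

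**The concern.** The success rate of the analysed endpoint is the chance of being upgrade-free *and* having a usable grade at Biopsy 2. The power statement uses only the first part. The two agree only if no upgrade-free man lacks that grade.

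The plan itself creates such men:

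- Under Protocol 6.8, any prostate cancer therapy, TURP or a 5-alpha-reductase inhibitor moves a man in either arm to the Follow-up Phase, whose assessment list contains no biopsy.
- Protocol 2.1.1 cites reasons other than grade for leaving surveillance (PSA doubling time 43.5%, patient preference 6%, against 35% for grade progression), though without a 36-month rate.
- Under Protocol 6.3.1, declining the first infusion or its leukapheresis means withdrawal from the study. This route exists only in the sipuleucel-T arm, so missingness need not be equal.
- A pre-withdrawal biopsy taken well before month 36 does not fill the Biopsy 2 slot.

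Replacement is not an allowance. It covers only sipuleucel-T men who were never infused, and SAP 9.1 keeps them in the intention-to-treat set.

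At stake is the reading of a null result: the stated power would be taken at face value although it was not computed for the test actually performed.

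**Working it through.** **Inputs from the documents.** 300 and 150 men; one-sided alpha 0.025; upgrading 0.16 and 0.30; missing grade counted as failure.

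**Step 1: reproduce the plan's figure.** Odds ratio = (0.84/0.16)/(0.70/0.30) = 2.25, as stated.

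Pooled z-test: power = Φ[(p_s − p_c − 1.96·SE0)/SE1].
- Pooled proportion = (300×0.84 + 150×0.70)/450 = 0.7933.
- SE0 = √[0.7933×0.2067×(1/300 + 1/150)] = 0.0405.
- SE1 = √[0.84×0.16/300 + 0.70×0.30/150] = 0.0430.
- Power = Φ[(0.14 − 1.96×0.0405)/0.0430] = Φ(1.41) = 92.1%.

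One-sided Fisher test by full enumeration gives 90.3%. The documents do not name their method; either supports the claim when nobody is missing. The exact value is closer to the planned test. The reserve above 90% is 0.3 points (exact) or 2.1 points (pooled).

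**Step 2: put the failure rule in.** Let m_s and m_c be the shares of otherwise upgrade-free men in the sipuleucel-T and control arms with no usable Biopsy 2 grade after the SAP 8.1.1 substitution. Men who have already upgraded fail anyway and add nothing. Then

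p_s = 0.84(1 − m_s), p_c = 0.70(1 − m_c).

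The documents give no value for m, so every non-zero rate below is an illustrative assumption.

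| m_s | m_c | p_s | p_c | Exact Fisher | Pooled z |
|---|---|---|---|---|---|
| 0 | 0 | 0.840 | 0.700 | 90.3% | 92.1% |
| 1% | 1% | 0.832 | 0.693 | 88.9% | 91.0% |
| 2% | 2% | 0.823 | 0.686 | 87.6% | 89.8% |
| 5% | 5% | 0.798 | 0.665 | 83.1% | 86.0% |
| 10% | 10% | 0.756 | 0.630 | 75.3% | 78.9% |
| 10% | 5% | 0.756 | 0.665 | 48.0% | 53.1% |
| 15% | 10% | 0.714 | 0.630 | 39.7% | 44.1% |
| 5% | 10% | 0.798 | 0.630 | 95.4% | 96.4% |
| 10% | 15% | 0.756 | 0.595 | 92.0% | 93.5% |

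In men, 2% in both arms is 0.02×252 ≈ 5 on sipuleucel-T and 0.02×105 ≈ 2 on control. At 10% in both arms the odds ratio is (0.756/0.244)/(0.630/0.370) = 1.82, down from 2.25.

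**Step 3: where 90% is lost.** With equal m, power crosses 90% at m = 0.2% (exact) or 1.8% (pooled). If m_s is 5%, m_c must be at least 7.2% (exact) or 6.4% (pooled) to keep 90%; if m_s is 10%, at least 14.1% or 13.4%.

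**Step 4: the planned test.** Simulating the exact CMH test in four strata (assumed mix 40/40/10/10%, with Grade Group 1 at its 80% cap; common rates across strata; 40,000 replicates) gives 90.3% with none missing, then 89.0%, 83.0% and 75.3% at an equal 1%, 5% and 10%. The unstratified Fisher figures are therefore a fair guide.

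**Step 5: a count from the SAP.** SAP 12.6.1.3 records three replaced sipuleucel-T men, who stay in the analysis set. Whether they had a Biopsy 2 is not stated. If they are three extra failures and nobody else is missing (303 against 150, p_s = 252/303 = 0.832), power is about 86% exact and 88% pooled.

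**The case against.** **This is an unstated assumption, not a calculation error.** True: the arithmetic is correct for upgrading alone. The objection does not make the result apply to the endpoint analysed.

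**The size and direction cannot be established.** All the missing rates are assumed, and the results run from about 40% to 96%. The study is open-label, and loss to treatment could be greater in control, which would raise power. The adverse unequal cases assume a five-point gap that nothing in the documents supports. This stands: the documents do not show that power is below 90%. They also do not show that it is at least 90%, which is what the SAP asserts.

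**The 0.30 might already include unobserved men.** Its source is not given, and Protocol 10.1 speaks of observation. But the text calls it a proportion upgrading, and 0.70 the proportion free of upgrading.

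**The thresholds look more precise than they are.** An m of 0.2% is less than one man (0.002×357 ≈ 0.7), and the inputs are approximate: control success of 0.71 instead of 0.70 alone gives 85.9/88.5%. Fair. The threshold shows only that there is almost no reserve.

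**The 450 may hold slack.** The pooled formula needs 417 for 90% power and the continuity-corrected one 447. No allowance is stated, and even the pooled surplus covers only 1.8% missing under the failure rule.

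**Mitigation exists.** Men consent to two biopsies, and prostatectomy and unscheduled histology go to central review, so some who leave for treatment are recorded as upgraded. Confidence intervals, last-observation-carried-forward and per-protocol analyses, and a plot of missingness are planned. These limit the harm when the result is read; they do not correct the stated figure.

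**Conclusion.** The concern holds. The power in the synopsis, Protocol 10.1 and SAP 6.2 is that of a test on upgrading in fully observed men, not of the primary analysis, in which a missing Biopsy 2 grade is a failure. Any equal missingness above 0.2% (exact) or 1.8% (pooled) of upgrade-free men takes power below 90%, and 5% to 10% takes it to roughly 75–86%. Those sizes rest on assumed rates and on missingness being independent of grade; with unequal rates power can fall much further or rise above 90%. That the figure is conditional on complete observation, without saying so, needs no assumed rate. This should be corrected, but it does not threaten the validity of the test.

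**What to change.** Amend the synopsis, Protocol 10.1 and SAP 6.2 in one of two ways.

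1. Add the condition, for example: *The 90% power assumes that no randomised man who is otherwise free of upgrade lacks a usable BICR grade at Biopsy 2 (scheduled, or substituted under SAP 8.1.1); such men are counted as failures in the primary analysis.*
2. Restate power for the endpoint as analysed. Give the sponsor's expected missing proportion among otherwise upgrade-free men in each arm, the resulting success rates, and the power of the planned exact stratified CMH test for those rates, with assumed rates labelled as such.

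The second is more informative, because it shows how far power depends on the balance of missingness between arms. The cost is wording in three places. The stated power becomes conditional or, probably, less favourable. Enrolment, endpoint and test do not change.

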6.3 Randomization

Eligible subjects will be randomized to the sipuleucel-T arm or control arms in a 2:1 ratio based on a predetermined, computer-generated randomization schedule. The randomization will be balanced by using block randomization.

Randomization will be stratified by:

- ISUP Grade Group (1 or 2)
- Number of biopsies within 12 months of Screening (1 or >1)

Randomization will take place across all clinical trial sites using an Interactive Response Technology (IRT). The IRT will assign a unique code, which will dictate the assignment to either sipuleucel-T arm or control arm. The requestor must use his or her own user identification and personal identification number when contacting the IRT and will then give the relevant subject details to uniquely identify the subject.

7.0 Study Endpoints, Variables and Covariates

7.1 Primary Endpoint

- Proportion of subjects without histological reclassification (Gleason group upgrade) within 36 months of randomization as determined by Blinded Independent Central Review (BICR)
 - Upgrade is defined as subjects at randomization with either International Society of Urological Pathology (ISUP) Grade Group 1 (Gleason 3+3) upgraded to Grade Group 2 (Gleason 3+4) or higher or subjects at randomization with Grade Group 2 upgraded to Grade Group 3 (Gleason 4+3) or higher.

7.2 Secondary Endpoints

7.2.1 Efficacy

Per the protocol, the secondary efficacy endpoints are:

- To determine the number of subjects with subsequent prostate cancer treatment (e.g., surgery, radiation, ADT) in each study arm
- Characterization of PROs by Memorial Anxiety Scale for Prostate Cancer (MAX-PC), Short Form 12 Health Survey (SF-12), The Expanded Prostate Cancer Index Composite for Clinical Practice (EPIC-CP), and International Prostate Symptom Score (IPSS) at baseline and 12-, 24-, and 36-month visits after randomization

The interpretations of these secondary efficacy endpoints based on the objectives, as assessed from baseline at the 12, 24, and 36 months visits post randomization, are as follows:

- Subsequent Prostate Cancer Treatment
 - Proportions of subjects with subsequent prostate cancer treatment
 - Time to the First Subsequent Prostate Cancer Treatment
- Patient Reported Outcomes (PROs). Will assess PROs at each collection point including change from baseline in the
 - MAX-PC total score and subscores for Prostate Cancer Anxiety, PSA Anxiety, and Fear of Recurrence,
 - SF-12 domain and QOL score and the SF-6D Quality adjusted Life Years index
 - EPIC-CP overall response and individual and pooled domain scores, and
 - I-PSS total scores, each of the urinary symptoms scores, and the quality of life due to urinary symptoms score.

7.2.2 Safety

Per the protocol, the secondary safety endpoint is:

- To evaluate safety by determining the incidence of adverse events (AEs), assessing laboratory data for clinically significant laboratory abnormalities, and evaluating physical examination (PE) findings in each study arm

The interpretation of this secondary safety endpoint is:

- Incidence of adverse events (AEs), including clinically significant laboratory abnormalities and physical examination (PE) findings reported as AEs.

7.3 Exploratory Endpoints

Per the protocol, the exploratory endpoints are:

- To calculate the correlation of prostate tissue and peripheral immune responses, as well as product parameters, to sipuleucel-T efficacy
- To determine in the cohort of subjects having a radical prostatectomy the number of subjects with an ISUP Grade Group change (up- or down-grade) determined by BICR from radical prostatectomy tissue histology in each study arm
- To measure the percentage of subjects with a negative biopsy at any post-randomization biopsy assessment in each study arm
- To compare the proportion of subjects with clinical risk group progression (e.g., Cancer of the Prostate Risk Assessment (CAPRA) and National Comprehensive Cancer Network (NCCN) prostate cancer risk groups) between study arms
- To calculate Prostate-specific antigen (PSA) velocity from randomization through study completion in each study arm
- To determine the association of prostate cancer tissue genomic profile and sipuleucel-T treatment

The interpretations of these exploratory endpoints are:

- Prostate tissue biomarkers, peripheral immune biomarkers, and sipuleucel-T product parameters by histological reclassification.
- Proportion of subjects with an ISUP Grade Group change (up- or down-grade) as determined by BICR from radical prostatectomy tissue histology in the cohort of subjects having a radical prostatectomy
- Proportion of subjects with a negative biopsy at any post-randomization biopsy assessment
- Proportion of subjects with clinical risk group progression (e.g., Cancer of the Prostate Risk Assessment (CAPRA) and National Comprehensive Cancer Network (NCCN) prostate cancer risk groups)
- Prostate-specific antigen (PSA) velocity from randomization through study completion
- Change in prostate cancer tissue genomic profile from baseline by treatment arm

8.0 Endpoint and Variable Definitions

Unless otherwise stated, baseline refers to the last assessment prior to randomization. Study day is defined as (study date – randomization date + 1).

8.1 Efficacy Endpoints

8.1.1 Proportion of Subjects Without Gleason Group Upgrade

A subject's baseline Gleason group is reported in the ISUP grade group field on the Screening Gleason CRF page. If multiple biopsies were performed during screening, the highest ISUP grade will be used as the baseline grade.

Post-randomization biopsies are scheduled between 12 and 18 months (Biopsy 1) and between 33 and 39 months (Biopsy 2) after randomization. Primary and secondary Gleason scores from BICR of these biopsies are recorded on the Prostate Biopsy Results CRFs in the Biopsy Screen and Biopsy Screen 2 folders, respectively. Per Epstein et al (1), post-randomization ISUP grade groups can be derived from the primary and secondary Gleason scores as follows:

- ISUP Grade Group 1 – sum of primary and secondary Gleason scores ≤ 6
- ISUP Grade Group 2 – primary Gleason score = 3 and secondary Gleason score = 4
- ISUP Grade Group 3 – primary Gleason score = 4 and secondary Gleason score = 3
- ISUP Grade Group 4 – sum of primary and secondary Gleason scores = 8
- ISUP Grade Group 5 – sum of primary and secondary Gleason scores = 9-10

There may also be unscheduled or end of study biopsies post-randomization, with ISUP grade groups recorded in the “What is the Final ISUP Score” field of the ISUP End of Study Change CRF located in the Unscheduled or Early Withdrawal/End of Study folders, respectively. These will be used as post-randomization ISUP grade groups if they cannot be derived from scheduled biopsy results and if they are based on BICR. Missing scheduled Biopsy 1 ISUP grade groups will be imputed with grade groups recorded within the subjects’ 12 month visit and 18 month visit dates and missing scheduled Biopsy 2 ISUP grade groups will be imputed with grade groups recorded within 90 days of the subjects’ 36 month visit date. If visit dates are missing, the nominal study date will be used. For example, if the 12 month visit date is missing, it will be imputed with the date of study day 360 (12*30 days).

A subject has a Gleason group upgrade if they had an ISUP Grade Group 1 at baseline and an ISUP Grade Group 2 or higher within 36 months post-randomization or if they had an ISUP grade group 2 at baseline and an ISUP Grade Group 3 or higher within 36 months post-randomization. The primary endpoint is the proportion of subjects in the treatment arm without ISUP Gleason group upgrade within 36 months of randomization. That is, success for this endpoint is defined as not having a Gleason group upgrade at Biopsy 1 or Biopsy 2, after being assessed at least through 36 months (Biopsy 2). Subjects upgrading before 36 months, those with an upgrade at Biopsy 2, or those with missing ISUP grade group at baseline or Biopsy 2 will be counted as failures.

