12.6 Efficacy Analyses

12.6.1 Primary Endpoint

The counts and proportions of subjects without ISUP Gleason group upgrade within 36 months of randomization will be presented by study treatment arm and overall. Exact 95% confidence intervals (CIs) for the proportions and the odds of no upgrade will also be presented. The reasons for failure (upgrade within 36 months) will be summarized as well. The exact Cochran-Mantel-Haenszel test of the null hypothesis of no difference in the odds of no ISUP grade group upgrade across treatment arms, while accounting for stratification by baseline ISUP grade group and number of biopsies, will be performed in the ITT analysis set.

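### SAP 8.1.1 contradicts itself and protocol 10.5.1 on a man whose only centrally read upgrade comes from an off-schedule biopsy

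*SAP*

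**What the plan says.** SAP 8.1.1 holds two sets of statements about the primary endpoint.

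The first set looks only at scheduled biopsies. It says that "success for this endpoint is defined as not having a Gleason group upgrade at Biopsy 1 or Biopsy 2", provided the man has been assessed through Biopsy 2. For unscheduled and end-of-study grades it says: "These will be used as post-randomization ISUP grade groups if they cannot be derived from scheduled biopsy results", and adds that they must rest on BICR. It then gives windows for filling a missing scheduled grade. For the second biopsy, "missing scheduled Biopsy 2 ISUP grade groups will be imputed with grade groups recorded within 90 days" of the 36-month visit. A missing visit date is replaced using 30-day months; in the SAP's example for the 12-month visit, "it will be imputed with the date of study day 360 (12*30 days").

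The second set is not limited to scheduled biopsies. For a man in Grade Group 1 at baseline, an upgrade is "an ISUP Grade Group 2 or higher within 36 months post-randomization". The failures are: "Subjects upgrading before 36 months, those with an upgrade at Biopsy 2, or those with missing ISUP grade group at baseline or Biopsy 2". SAP 7.1 defines the endpoint as "Proportion of subjects without histological reclassification (Gleason group upgrade) within 36 months of randomization", and SAP 12.6.1 reports "The counts and proportions of subjects without ISUP Gleason group upgrade within 36 months of randomization".

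Protocol 10.5.1 defines upgrading as a BICR finding at any biopsy after randomization. It says status is assessed at scheduled biopsies, at prostatectomy or at another time. Its list of failures is: upgrade before 36 months, upgrade at Biopsy 2, or no Biopsy 2 completed before 39 months.

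**The concern.** This is the only confirmatory endpoint, and SAP 12.6.1.2 rests the success of the study on one test of it. A programmer who works from the success sentence and the unscheduled-grade rule scores an off-schedule upgrader as a success. One who works from the failure sentence scores him as a failure. No sentence says which rule governs when scheduled grades exist and an off-schedule BICR grade is higher.

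Such a man can occur. Protocol 8.11 sends unscheduled biopsies to BICR. It also keeps an upgraded man in the Active Phase if he stays on surveillance, so he can reach Biopsy 2.

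The trial is open-label and the number of unscheduled biopsies is not fixed, so their frequency could differ by arm. A rule that depends on whether a biopsy was scheduled could then act differently in the two arms.

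**Working it through.** **1. Classification.** Each man below has one off-schedule BICR upgrade and no treatment before Biopsy 2, except where noted.

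| Pattern | SAP success sentence, with substitution | SAP failure sentence | Protocol 10.5.1 |
|---|---|---|---|
| Biopsies 1 and 2 not upgraded; off-schedule upgrade at month 15, 24 or 35 | success | failure | failure |
| Biopsy 1 missing, Biopsy 2 not upgraded; upgrade at month 24 | success | failure | failure |
| Biopsy 1 missing, Biopsy 2 not upgraded; upgrade at month 15 (substituted as Biopsy 1) | failure | failure | failure |
| Biopsy 2 missing, for example after prostatectomy; upgrade at month 24 or 35 | failure | failure | failure |
| Biopsies 1 and 2 not upgraded; upgrade at month 37 | success | not reached (limit is 36 months) | failure by its any-biopsy definition |

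The conflict is in rows 1 and 2. Row 5 is a question of cut-off: the protocol's any-biopsy definition has no time limit, but its list of failures stops at 36 months or Biopsy 2.

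**2. The plan's power.** Inputs from SAP 6.2: 300 and 150 men, success 0.84 and 0.70, one-sided alpha 0.025.

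- Odds ratio = (0.84/0.16)/(0.70/0.30) = 2.25, as stated.
- Fisher's exact test, full enumeration of two binomials: power 0.903. The stated 90% is reproduced.
- With no true effect (0.70 in both arms), this test rejects with probability 0.020; it is conservative against the nominal 0.025.

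Fisher's test is an unstratified stand-in for the planned exact CMH test.

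**3. Size of the effect under the literal success sentence.** Let f1 and f0 be the shares of upgraders in the sipuleucel-T and control arms who are upgraded only off-schedule. Both are assumptions. The observed success proportions become

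ps = 0.84 + 0.16 × f1 and pc = 0.70 + 0.30 × f0.

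Equal shares, design effect:

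| f1 = f0 | Men affected (sipuleucel-T / control) | ps | pc | Odds ratio | Power |
|---|---|---|---|---|---|
| 0 | 0 / 0 | 0.840 | 0.700 | 2.25 | 0.903 |
| 2% | 1.0 / 0.9 | 0.843 | 0.706 | 2.24 | 0.895 |
| 5% | 2.4 / 2.3 | 0.848 | 0.715 | 2.22 | 0.882 |
| 10% | 4.8 / 4.5 | 0.856 | 0.730 | 2.20 | 0.858 |

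Men affected = 300 × 0.16 × f1 and 150 × 0.30 × f0.

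No true effect, 0.70 in both arms, one-sided rejection rate:

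- 5% in the sipuleucel-T arm only: 0.70 + 0.30 × 0.05 = 0.715 against 0.700; rate 0.041.
- 5% in the control arm only: 0.700 against 0.715; rate 0.008.
- None: 0.020.

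**4. The substitution window (minor).** With a month of 30.4375 days, 39 months is 1187.1 days after randomization.

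- Visit date known: the 36-month visit has a window of 14 days either side (protocol Tables 1 and 2). The latest substitute is 1095.75 + 14 + 90 = 1199.75 days, about 13 days past 39 months.
- Visit date missing: 36 × 30 = study day 1080, plus 90 = study day 1170. SAP 8.0 counts randomization as day 1, so this is 1169 days after randomization, and 1187.1 − 1169 = about 18 days before 39 months.

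**The case against.** The best defence is that the success sentence is a gloss. It opens as a restatement of the sentence before it, which speaks of upgrade within 36 months, and the sentence after it lists upgrades before 36 months as failures with no limit to scheduled biopsies. SAP 7.1, SAP 12.6.1 and the last-observation-carried-forward analysis in SAP 12.6.1.3 use the same within-36-months idea. The unscheduled-grade rule could also be read assessment by assessment, so that a month-24 grade is one that the scheduled biopsies cannot supply.

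That reading is reasonable and probably the intended one, but the text does not compel it. The success sentence presents itself as the definition, and the unscheduled-grade rule limits which grades enter the derivation. If that rule also governs the failure sentence, the SAP becomes consistent with itself but departs from protocol 10.5.1. Either way a correction is needed.

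The objection on size stands. The man must be upgraded off-schedule, stay untreated and have a Biopsy 2 grade without upgrade. Protocol 2.1.1 presents Gleason upgrading as a reason to switch to active treatment. Treated men leave the Active Phase under protocol 6.8 and, without a Biopsy 2 grade, fail anyway.

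A reader might infer that the rule favours sipuleucel-T or inflates the type I error. The documents do not support that. They give no rate of unscheduled biopsies in either arm. The 0.041 needs 5% in one arm and none in the other, and the reverse split gives 0.008.

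A reader might also infer that men with a cancer-free Biopsy 2 are scored as failures, since SAP 8.1.1 has no category for them. That depends on CRF coding that the documents do not show. If such a biopsy is coded 0+0, the sum is at most 6, it falls in Grade Group 1, and nothing is lost.

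**Conclusion.** The contradiction stands and should be fixed. Followed literally, two sentences of SAP 8.1.1 pass a man whom the section's own failure sentence (for upgrades before 36 months) and protocol 10.5.1 fail.

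The effect is probably small. At equal shares of 2% to 10%, power is 0.895 to 0.858 against 0.903, with about one to five men affected per arm. Bias requires unequal shares, and its direction is unknown. All shares are assumptions, and the figures come from an unstratified proxy for the planned test. The case for acting is that the rule decides the single confirmatory endpoint and should be settled before the data are analysed. The window mismatch is a minor matter, and the cancer-free case is only conditional.

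**What to change.** In SAP 8.1.1:

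1. State that a BICR-determined upgrade from baseline on any post-randomization tissue (scheduled, unscheduled, early-withdrawal or prostatectomy), up to 36 months or up to and including Biopsy 2, whichever is later, is a failure whatever the scheduled results show. Keep the existing failures for a missing baseline or Biopsy 2 grade.
2. State that the rule on unscheduled and end-of-study grades only fills missing scheduled grades and does not limit which biopsies can show an upgrade.
3. Reconcile this cut-off with the any-biopsy wording of protocol 10.5.1 for upgrades found after Biopsy 2. For example, a man with Biopsy 2 at month 34 and an upgrade at month 38 passes under item 1 but fails under that wording.

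Minor additions: use the protocol's 33 to 39 calendar-month window for Biopsy 2 and for its substitute, in place of the 90-day and 30-day-month rules. Check the CRF; only if it leaves the Gleason fields blank for a cancer-free biopsy, state that a completed Biopsy 2 read by BICR as free of cancer is evaluable and is not an upgrade.

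The cost is a few sentences of SAP text and one derivation rule. No new data are needed, because protocol 8.11 already sends unscheduled and prostatectomy slides to BICR during the Active Phase. After an early Biopsy 2, a later upgrade counts only if a BICR grade exists, which the words BICR-determined cover.
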